### 11.5.1.4 Probable symptomatic hypoglycemia

Probable symptomatic hypoglycemia is an event during which symptoms of hypoglycemia are not accompanied by a plasma glucose determination, (but that was presumably caused by a plasma glucose concentration  $\leq 3.9$  mmol/L [ $\leq 70$  mg/dL]), i.e., symptoms treated with oral carbohydrate without a test of plasma glucose.

### 11.5.1.5 Relative hypoglycemia

Relative hypoglycemia is an event during which the patient reports typical symptoms of hypoglycemia, and interprets the symptoms as indicative of hypoglycemia, but with a measured plasma glucose concentration  $> 3.9$  mmol/L ( $> 70$  mg/dL).

Figure 1 - Hypoglycemia classification in Study PDY15079

### 11.5.2 Instructions for the management of DKA in diabetic patients

Diabetic ketoacidosis, including atypical (euglycemic) DKA, is the most serious emergency in patients with T1D and T2D. It is possible that GI or other AEs occurring with sotagliflozin may mask presenting symptoms of DKA. Because sotagliflozin lowers blood glucose by insulin independent SGLT1 and SGLT2 inhibition, it is possible for DKA to be present with normal or low blood glucose. Therefore, the Investigator must still consider a DKA event even if blood glucose is low or normal. Please refer to [Appendix D](#) for further details regarding DKA.

## 12 HANDLING OF SUBJECT WITHDRAWAL

### 12.1 LIST OF TREATMENT WITHDRAWAL CRITERIA

Refer to [Section 11.3.3](#) for cases in which AESI lead to treatment discontinuation.

Pregnancy will lead to permanent treatment discontinuation in all cases (Refer to [Section 11.3.3](#)).

### 12.2 REASONS FOR TREATMENT WITHDRAWAL

- The patient may withdraw from the treatment if they decide to do so, at any time and irrespective of the reason, or upon the Investigator's decision or at the specific request of the Sponsor.
- However, withdrawal of consent for treatment should be distinguished from withdrawal of consent for follow-up visits. Patient who withdraws should be explicitly asked about the contribution of possible AEs to their decision to withdraw consent, and any AE information elicited should be documented. Such information about the reason of patient's withdrawal will be filled in in the appropriate eCRF page.
- In case of withdrawal, preferably the patient should withdraw consent in writing and, if the patient or the patient's representative refuses or is physically unavailable, the site should document and sign the reason for the patient's failure to withdraw consent in writing. The informed consent for the study should note that although a patient is free to leave the study and stop taking study medication, the investigators hope the patient will remain for follow up status evaluations.

### 12.3 REPLACEMENT OF PATIENTS

According to the study design, a patient who prematurely ends his/her study period after the start of the baseline period and who received treatment may be replaced in order to have 81 patients who have completed a minimum of 12 days treatment with IMP (sotagliflozin or placebo).

In the case of a discontinuation related to an AE, the replacement may be discussed between the Investigator and the Sponsor.

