	
other major systemic disease (including any diseases with evidence of malabsorption), making interpretation of the protocol and/or the interpretation of the study results difficult
 
E13. Known allergies, hypersensitivity, or intolerance to sotagliflozin or any inactive component of sotagliflozin or placebo (i.e., microcrystalline cellulose, croscarmellose sodium [disintegrant], talc, sodium oxide, and magnesium stearate [non-bovine]), unless the reactions deemed relevant to the study by the PI
 
E14. Laboratory findings at the Screening Visit:
 
 
Alanine aminotransferase (ALT) or aspartate aminotransferase (AST) >3 times the upper limit of the normal laboratory range (ULN) (1 repeat allowed)
 
Total bilirubin >1.7 times the ULN (except in case of Gilbert's syndrome) (1 repeat allowed)
 
Amylase and/or lipase > 3 times the ULN (1 repeat allowed)
 
 
E15. Patients with a severe or persistent despite of optimal treatment genitourinary tract infection at time of randomization.
 
E16. Patients the Investigator or any Sub-investigator, research assistant, pharmacist, study coordinator, other staff or relative thereof directly involved in the conduct of the protocol
 
Additional exclusion criteria for patients with diabetes
 
E17. History of diabetic ketoacidosis or non-ketotic hyperosmolar coma within 3 months prior to the screening visit
 
E18. Lower extremity diabetic complications (such as skin ulcers, infection, osteomyelitis and gangrene) identified during the Screening period, and still requiring treatment at Randomization

Total expected number of patients:
 
Expected number of sites:
	
Approximately 64 patients completing treatment will be enrolled.
 
Up to 15 sites

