## 6 STUDY DESIGN

### 6.1 DESCRIPTION OF THE STUDY

This is a phase 2, multi-center, multinational, randomized, double-blind, placebo-controlled, parallel arm trial of the safety, tolerability and pharmacodynamic activity of sotagliflozin in hemodynamically stable patients with worsening heart failure. Study drug will be initiated in the hospital or other appropriate setting such as heart failure or infusion unit, after completion of intravenous diuretic therapy, and continued in an outpatient setting for a total of fourteen days. The main pharmacodynamic endpoints studied are changes in plasma volume and total body water as measured by indicator dilution methods using I-albumin and deuterium oxide, and hemoconcentration as measured by changes in hematocrit, hemoglobin, plasma total protein and plasma albumin levels.

An initial cohort of patients (Cohort 1) will receive sotagliflozin 200mg (n approximately 10) or placebo (n approximately 5) for fourteen days. Following safety monitoring and review by the DMC, Cohort 2 will receive sotagliflozin 400mg (n approximately 10) or placebo (n approximately 5) orally for fourteen days. Following completion of Cohort 2 and review of safety and tolerability by the DMC, conduct of cohort 3 will commence where patients will be allocated to sotagliflozin 400 mg (n approximately 17) or placebo (n approximately 17) orally for fourteen days. This is summarized in [Table 1](#).

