## 8 SELECTION OF PATIENTS

### 8.1 NUMBER OF PATIENTS PLANNED

The study population will consist of male and female patients, 18 years and older, admitted to the hospital or heart failure unit or infusion center with worsening of heart failure requiring administration of intravenous diuretics, as per inclusion and exclusion criteria detailed below.

A subject who received treatment and prematurely ends his/her treatment will be replaced in order to have approximately 64 evaluable observations.

A patient should not be randomized more than once.

Re-screening is allowed once during the current hospitalization, if in the opinion of the investigator, the change in the clinical status of the patient allows inclusion in the trial. Patients that failed screening during the first encounter for this trial can be rescreened during subsequent hospitalizations or visits to the infusion or heart failure units.

A patient that requires re-hospitalization will be discontinued from IMP administration. Every effort will be made to follow up the progress of the patient and continue collection of relevant safety data, as appropriate and when applicable, and as judged by the Investigator with potential input from the DMC and Sponsor, as appropriate for each case, for the same follow up period (approximately 2 weeks) as for all other patients participating in the trial. In those cases, the follow up procedures and/or visit to clinical site should be followed as per study flow chart in [Section 1.2](#). Only if judged appropriate by the Investigator and Sponsor, and in the absence of safety signals, the patient will be allowed to participate in some or all of the EOT study procedures.

For all patients, GFR will be calculated from the serum creatinine (sCr; mg/dL) and age (years) via the abbreviated Modification of Diet in Renal Disease (MDRD) equation (20):

$$GFR = 186 (sCr)^{-1.154} (age)^{-0.203} (1.212 \text{ if black}) (0.742 \text{ if female})$$

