## 9.4 METHOD OF ASSIGNING PATIENTS TO TREATMENT GROUP

The randomized treatment kit number is generated centrally by Sanofi. The IMPs are packaged in accordance with this list.

At the Screening Visit, the Investigator or designee has to contact the IRT to receive the patient number. [REDACTED]

Before randomizing a subject on Day 1, the Investigator or designee should check if patients comply with all inclusion/exclusion criteria. At day 1, the IRT is contacted for randomization and corresponding allocation of treatments package. Patients are randomized to receive either sotagliflozin or placebo, according to the randomization scheme for each Cohort as described below:

Cohort 1: Sotagliflozin 200 mg: Placebo 2:1

Cohort 2: Sotagliflozin 400 mg: Placebo 2:1

Cohort 3 (as amended here): Sotagliflozin 400 mg: Placebo 1:1

For each randomized patient, the IRT will allocate a treatment package number corresponding to the treatment group assigned.

A randomized subject is defined as a subject who is registered and assigned with a treatment kit number from the IRT, as documented in IRT.

A subject cannot be randomized more than once in the study.

A patient can be rescreened once in case of manageable exclusion as deemed by the Investigator. In these cases, a patient will need to sign a new ICF, be registered as a new patient in IRT, and assigned a new patient number in IRT (first Screening Visit is to be registered as a screen failure in IRT), and complete the Screening Visit procedures/assessments again.

Potential replacement patients will have a patient number assigned from IRT and the patient number that is replaced will be recorded in IRT and transferred to the case report form. Each patient will receive the same treatment and treatment sequence as the withdrawn patient. See also [Section 12.3](#).

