#### 10.3.2 Number of pharmacokinetic samples

**Table 9 - Number of plasma samples**

	sotagliflozin
By subject	7
Total by subject	7
Total for cohort 1 and 2 only (30 planned)	210

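### Protocol Section 12.3 still sets a replacement target of 81 completers where Section 8.1, the synopsis, Table 1 and Table 6 give about 64, and Sections 8.1 and 12.3 differ in force and in the unit counted

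*Protocol*

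**What the plan says.** Two sections of the current protocol state a replacement rule.

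- Section 8.1: "A subject who received treatment and prematurely ends his/her treatment will be replaced in order to have approximately 64 evaluable observations".
- Section 12.3: a patient who received treatment and ends early "may be replaced in order to have 81 patients who have completed a minimum of 12 days treatment with IMP". It adds: "In the case of a discontinuation related to an AE, the replacement may be discussed between the Investigator and the Sponsor".

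The planned size is stated elsewhere in the same document.

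- Synopsis, expected number of patients: "Approximately 64 patients completing treatment will be enrolled".
- Section 6.1, on cohort 3: "patients will be allocated to sotagliflozin 400 mg (n approximately 17) or placebo (n approximately 17) orally for fourteen days".
- Table 1: cohorts of 15, 15 and 34, total 64.
- Table 6: sample totals computed for about 64 patients.

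Section 9.4 describes how a replacement is made. The number of the patient being replaced is recorded in the IRT, and the new patient receives the withdrawn patient's treatment. It cross-refers to Section 12.3.

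**The concern.** A replacement rule needs a target, a definition of who counts towards it, and a statement of whether replacement is required or optional. The current protocol gives two answers to each. Early stops are foreseeable here, because Sections 7.2.1 and 8.1 both take re-hospitalized patients off IMP, so the rule is likely to be used. Someone handling a replacement under Section 9.4 is directed to Section 12.3, which holds the one figure that does not fit the design. What is at stake is consistent operation. Two sites could treat the same early stop differently, and the report would have no single target against which to account for replacements.

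**Working it through.** **1. Reproduce the plan's current total.** Inputs are from protocol Table 1.

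- By cohort: 15 + 15 + 34 = 64.
- By arm: 10 (200 mg) + 27 (400 mg) + 27 (placebo) = 64.
- Table 6, albumin samples: 768 / 12 per patient = 64.
- Table 6, deuterium samples: 256 / 4 per patient = 64. With 81 patients these totals would be 972 and 324.

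So 64 reproduces in every way the current protocol allows, and 81 in none.

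**2. Find where 81 comes from.** SAP Section 1.1, written for the protocol as amended on 14 March 2018, has a three-arm cohort 3 of 17 + 17 + 17 = 51.

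- By cohort: 15 + 15 + 51 = 81.
- By arm: 27 + 27 + 27 = 81.
- Gap: 81 - 64 = 17, the size of the cohort 3 arm at 200 mg that the current amendment removed.

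As a cross-check, SAP Section 1.3 gives 71% power for 81 patients. A one-sided t-test at 0.05 with SD 0.8 L, a difference of 0.9 x 0.47 = 0.423 L, and 54 against 27 patients gives 71.9%. The figure 81 is therefore the three-arm sample size.

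**3. What 81 would mean if taken literally.** Cohorts 1 and 2 are planned at 15 + 15 = 30.

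- Cohort 3 completers needed: 81 - 30 = 51, against 34 planned.
- Excess: 17 / 64 = 26.6% of the study, or 17 / 34 = 50% of cohort 3.
- At 1:1 allocation: 51 / 2 = 25.5 per arm instead of 17.

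**4. Whether replacement could reach 81.** Under Section 9.4 each replacement takes the place of one identified withdrawn patient. If a patient who already counts as complete is not also replaced, each planned place yields at most one completer. The ceiling is then the number of planned places, about 64.

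**5. The two rules side by side.**

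| Element | Section 8.1 | Section 12.3 |
|---|---|---|
| Target | about 64 | 81 |
| Force | mandatory | optional |
| Unit counted | evaluable observation, not defined | at least 12 days of IMP |
| Stop for an AE | no separate provision | replacement open to discussion with the sponsor |

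The synopsis adds a third unit, patients completing treatment. Correcting the number in Section 12.3 would leave the other three rows unreconciled.

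**The case against.** The strongest reply is that this is one stale number with no practical reach. Cohort 3 is given as about 34 in the synopsis, the graphical design, Section 6.1 and Table 1. Randomization is central, with the scheme supplied to the IRT by the study biostatistician (Section 9.3.1). The current sample size is empirical (Section 14.1), so no power statement in the protocol depends on 81. All of this stands, and it limits the consequence. It does not make 81 correct or explain which rule governs.

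Four stronger readings are tempting, and the documents do not support them.

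- A reader might infer that sites and the IRT cannot tell when cohort 3 is full. Its planned size is consistent throughout, and nothing links the IRT cap or cohort closure to Section 12.3. Section 9.4 cross-refers to 12.3 but does not rank it above 8.1.
- A reader might infer that 17 more patients will be exposed. Section 12.3 only governs replacement and opens no new places.
- A reader might infer that a patient who stops on Day 12 counts as complete under 12.3 but must be replaced under 8.1. That is one reading. Section 8.1 defines neither a premature end nor an evaluable observation, so the 12-day minimum could be taken as the missing definition. SAP Section 2.4 also uses 12 to 15 days as its top exposure band.
- A reader might infer that discretion over AE-related replacement biases the completer set. No bias is shown. Completing 12 days does not define an analysis population. Every randomized and exposed patient stays in the safety population (Section 14.3.1), and replacing a patient does not change that patient's own eligibility for the PD population (Section 14.3.3).

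**Conclusion.** The contradiction is real and sits in current protocol text. Section 12.3 carries a target of 81 that belongs to the superseded three-arm cohort 3, against 64 everywhere else that the current protocol states a total. The discrepancy is 17 completers. The step from 34 to 51 in cohort 3 shows only what the wording literally implies. It is not a forecast, because one-for-one replacement cannot deliver it. This rests on reading Section 9.4 as one replacement per withdrawn patient, and on not replacing anyone who already counts as complete.

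The differences in force, in the unit counted and in the treatment of AE-related stops are also real, and they would remain after the number is corrected. The documents support a finding of inconsistent replacement rules. They do not support a finding of uncertain cohort size, over-enrolment or biased analysis sets.

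**What to change.** In Section 12.3, replace 81 with approximately 64, given by cohort as 15/15/34.

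Then reconcile Sections 8.1 and 12.3 and the synopsis so that all three use:

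- one verb, stating whether replacement is required or optional;
- one definition of an evaluable or completed patient, including whether the 12-day minimum is that definition;
- one statement on replacement after an AE-related discontinuation. Case-by-case discussion can stay if the sponsor wants it, but both sections must say so.

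The cost is a wording change in two sections and the synopsis, made through the protocol's own amendment procedure (Section 18). It needs no extra patients or data collection.

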### 12.4 TREATMENT WITHDRAWAL FOLLOW-UP PROCEDURE

All study treatment withdrawals should be recorded by the Investigator on the appropriate case report form pages or screens for eCRF when considered as confirmed.

If possible, patients are to be assessed using the procedure planned for the end-of-study visit, including a pharmacokinetic sample if appropriate.

For any patient who fails to return to the site at the EOT visit, unless the patient withdraws the consent for follow-up, the Investigator should make every effort to contact the patient (eg, contact the patient's family or private physician, review available registries or health care database), and to determine his/her health status, including at least his/her vital status. Attempts to contact the patient must be documented in the patient's records (e.g., times and dates of attempted telephone contact, receipt for sending a registered letter).

Patients withdrawn from the study must not be re-included in the study. Their inclusion and treatment numbers must not be reused.

## 13 STUDY PROCEDURES

### 13.1 VISIT SCHEDULE

The visit schedule and procedures/assessments are listed in the Study Flow Chart ([Section 1.2](#)). The aim of this section is to provide details on how some of the procedures/assessments should be performed. All data obtained during the trial visits are reviewed by the Investigator and/or Sub-Investigators who are qualified in the treatment of heart failure patients and are familiar with the study.

#### 13.1.1 Screening procedures

Patients will undergo Screening assessments at Visit 1 (Day -21 to Day -1, and up to randomization on D1, to allow, for example, cases where the patient may be admitted and likely to be discharged on the same day) following signing of the informed consent form. The patient will receive information on the study objectives and procedures from the Investigator. The patient will have to sign the informed consent prior to any action related to the study.

The interactive response technology system (IRT) will be contacted at Visit 1 for notification of Screening Visit and to obtain the patient identification number.

Screening will include the investigations listed in the Study Flow Chart ([Section 1.2](#)) and detailed in [Section 10.2](#).

All patients must have a documented echocardiogram, either performed during Visit 1 or within 12 months from current admission or screening.

Rechecking of any parameters at screening is subject to the Investigator's judgment, allowed once.

Patients who meet all the inclusion criteria and none of the exclusion criteria will be eligible for randomization.

#### 13.1.2 Inclusion procedures

Inclusion procedures will be carried out during Screening (D-21 to D-1) or D1, as appropriate for each patient. Those will include the investigations listed in the study flow chart ([Section 1.2](#)) and detailed in [Section 10.2](#).

Baseline parameters may be rechecked once, at the Investigator's discretion. Results of a rechecked value should be known before the inclusion. The last value should be considered as the baseline value and reported in the case report form.

Prior to final inclusion and randomization, all patients must have completed the last planned IV administration (bolus or infusion), and *either* have commenced oral diuretic therapy *or* have a clear and documented plan to commence oral diuretic therapy. Patients may be discharged and return for Day 1 procedures within seven (7) days from discontinuation of IV diuretic administration.

Final inclusion and randomization, as appropriate, will be performed just before commencement of procedures on Day 1. Each patient will receive an incremental identification number corresponding to his/her order of enrollment in the study.

### 13.1.3 Description by type of visit

#### 13.1.3.1 Visit 2 (Day 1) (Inpatients or Outpatients returning for Day 1 procedures)

Eligible patients will be randomized on Day 1.

Day 1 procedures may be carried out in hospital wards or outpatient units. Please refer to the period flow chart in [Section 1.3](#) for the list of safety and baseline laboratory assessments procedures on Day 1.

The procedures for the assessment of the pharmacodynamic endpoints are described in detail in [Section 10.1.2.1](#) and [Section 10.1.2.2](#).

All eligible patients will have hemoconcentration samples obtained and total body water (deuterium oxide) assessment performed as per [Section 10.1.2.1](#). Deuterium is a stable isotope of hydrogen, abundant in nature and does not pose any radiation or health risk. No special facilities are required for the handling, administration and/or disposal of deuterated samples or solutions.

Sites that have the capacity to perform the additional plasma volume assessment by the I-albumin indicator dilution method will follow the procedure described in [Section 10.1.2.2](#). Sites using the I-albumin indicator dilution method should follow their institutional guidelines for the type of facility required to handle, administer, and dispose of radioactive material. The maximum dose of I-albumin used for the indicator dilution method of plasma volume determination is 25 µCi and within US is listed as 'exempt' on air regulations. Each blood sample collected during the procedure will contain < 0.1 µCi of radiation.

Patients will be treated with IMP (sotagliflozin or placebo) for 14 days, commencing on Day 1. IMP administration outside of site visits should take place in the morning between 7 AM and 11 AM daily for the duration of the treatment period. Meals should be taken approximately 15 minutes after IMP administration.

For safety and practical reasons, before any of the procedures or IMP administration on Day 1 (and depending on the site and choice of whether to perform direct or indirect plasma volume/hemoconcentration measurements), an indwelling catheter will be inserted in a peripheral vein of the forearm in order to obtain blood samples.

For patients eligible for discharge from hospital or unit: The patient diary is dispensed during day 1 and instructions/training on its use and completion are provided: Adverse events (AE), Concomitant medications, IMP intake (and whether it was taken before breakfast) and BP measurements (and time) are recorded on a daily basis between Day 2 and last follow up.

The automated BP monitors will also be dispensed on Day 1 and patients will be trained in their use. The technique employed should observe the following (described in detail in [Appendix C](#)):

1. First time (performed on Day 1 by the Investigator or qualified site staff): Determine the arm with higher BP (based on SBP) and evaluate for inconsistency of BP between arms to exclude major vascular problems
2. Day 2 until last follow up:
  - Measurements should take place, to the extent possible, within the same time window each day and preferably in the morning between 6 AM and 10 AM.
  - BP obtained after 5-10 minutes in the sitting resting position
  - Measurements should be done in triplicate, not less than 1-2 minutes between readings, and all measurements recorded in the Diary.
  - The same arm, as determined on Day 1 (unless it becomes uncomfortable or contraindicated due to a newly developed skin, musculoskeletal or other condition) should be used throughout the study

Entries in the diary (such as AE and IMP intake, and if not recorded in source documents, concomitant medications and BP) will also be recorded for patients that have not been discharged.

If BP monitoring is not standard, recordings using the BP monitor provided by the Sponsor or other appropriate monitor should be used to obtain BP readings. If the patient is discharged, they will be reminded to continue with diary updates as described above.

